6.6 Pharmacokinetic Analyses

Population PK analysis of telaglenastat will be performed for the PK-evaluable population, defined as all CB-Cabo patients who have received at least one dose of telaglenastat and have at least one evaluable PK sample. Individual PK concentrations will be tabulated and summarized. Descriptive statistics will include means, medians, ranges, and SDs, as appropriate.

The impact of telaglenastat on the PK exposure of cabozantinib will be evaluated by comparing the CB-Cabo arm with that of the Pbo-Cabo arm.

Additional PK analyses will be conducted as appropriate, on the basis of the availability of data. A separate report will include these additional analyses as well as details of population PK analyses.

6.7 Safety Analyses

Unless specified otherwise, safety analyses described in this section will be conducted for the Safety population, with patients grouped according to whether they received any telaglenastat treatment.

6.7.1 *Exposure of Study Medication*

Study drug exposure status for each component of the study drug, which include treatment duration, total dose received (mg), number of cycles, number of patients with dose adjustment and the reasons will be summarized for each treatment arm for the Safety population.

6.7.2 *Adverse Events*

Verbatim description of AEs will be mapped to Medical Dictionary for Regulatory Activities (MedDRA) preferred terms and system organ classes, and graded by the investigator according to NCI CTCAE v4.03. Treatment-emergent adverse events (TEAEs) will be summarized by mapped term, appropriate thesaurus level, NCI CTCAE grade, and treatment arm. In addition, serious adverse events, severe adverse events

(Grade ≥ 3), and adverse events leading to study drug discontinuation or interruption will be summarized accordingly. These tables will also be presented for TEAEs judged to be related (probably or possibility) to the study treatment. Multiple occurrences of the same event in a given patient will be counted once at the maximum grade. All deaths are reported as SAEs per study conduct. In order to accurately summarize the true SAE rate, all SAE summaries will not count Grade 5 events for patients who died due to progressive disease.

Per protocol and study conduct, safety follow-up is 28 days from date of last study drug administration or until initiation of a new anti-cancer therapy if earlier. For reporting purposes, “treatment emergent” is defined as new adverse events occurring on or after the first dose of study drug is administered until the clinical cutoff date, or existing events that worsened after the first dose during the study.

All listings of adverse events will also include all adverse events.

Deaths reported during the study treatment period and the follow-up period after treatment discontinuation will be listed by treatment arm.

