9.4.1 Safety

Please refer to the current CB-839 Investigator's Brochure for the most recent safety information for CB-839 monotherapy and CB-839 in combination regimens.

CB-839 Monotherapy

Treatment-related AEs for patients enrolled on Study CX-839-001 who received monotherapy with CB-839 on the BID fed regimen are presented in [Table 9.5-1](#). Of 88 safety-evaluable patients, 61 (69.3%) experienced AEs that were considered possibly or probably related to CB-839. The most frequent CB-839-related AEs were fatigue, gastrointestinal AEs (e.g., nausea, decreased appetite, and vomiting), liver function test (LFT) elevations (e.g., AST, ALT), and photophobia. These AEs were typically mild to moderate in intensity (Grade 1/2), reversible, and manageable without dose interruption or modification.

The most frequent Grade 3 AEs were elevations in LFTs, including AST, ALT, and alkaline phosphatase. Gamma-glutamyltransferase elevations were also noted but are of unclear clinical significance. The frequency of Grade 3 elevations in LFTs was limited, with 2 of 88 patients experiencing a treatment-related Grade 3 AST or ALT elevation. One Grade 3 AE of anemia was also considered to be possibly related to CB-839 (not shown). There have been no reported Grade 4 or Grade 5 treatment-related adverse events.

Table 9.5-1: CB-839 Related Adverse Events in $\geq 5\%$ of Patients Treated with Monotherapy CB-839 on the BID Schedule on Study CX-839-001

BID fed - Monotherapy (N=88)		
MedDRA Preferred Term	Number (%) of patients	
	All Grades	Grade 3
Patients with Any CB-839-Related AE	61 (69.3)	3 (3.4)
Fatigue	22 (25.0)	0
Nausea	20 (22.7)	0
Alanine aminotransferase increased	13 (14.8)	2 (2.3)
Photophobia	12 (13.6)	0
Aspartate aminotransferase increased	10 (11.4)	1 (1.1)
Decreased appetite	7 (8.0)	0
Gamma-glutamyltransferase increased	7 (8.0)	2 (2.3)
Blood alkaline phosphatase increased	6 (6.8)	1 (1.1)

Vomiting	5 (5.7)	0
23July2017 data cut		

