Photophobia and related ocular toxicities (e.g., photopsia) have been identified as CB-839-related events. In all but one case, these events have been Grade 1 and without impact on patients' daily lives. One photophobia event was characterized as Grade 2. These events appear to occur around C_{max} (1-4 hr after dosing) and resolve over a few hours. These events have been reported to become less frequent over extended dosing. Note: Photophobia/photopsia should be carefully distinguished from "photosensitivity". "Photosensitivity", which refers to an adverse event of the skin such as an unexpected sunburn or dermatitis on sun-exposed skin, has not been observed with CB-839 monotherapy or in combination with cabozantinib.

CB-839 in Combination

CB-839 has been combined in Phase 1 studies with standard of care therapies in a number of different solid tumors, including everolimus (N = 27), cabozantinib (N = 12), paclitaxel (N = 49), nivolumab (N = 82), and erlotinib (N = 1). In all cases thus far, the Adverse Event profile of CB-839 administered at 600-800 mg BID together with the full dose of each partner agent has been similar to those previously reported for each agent alone. Additional details are available in the Investigator's Brochure.

CB-839 + Cabozantinib

Based on the data cut on 23 October 2018 for patients enrolled on the phase 1 Study CX-839-001, treatment-related AEs reported for ≥ 2 patients among 13 patients receiving CB-839 (6 at 600 mg BID and 7 at 800 mg BID) with cabozantinib 60 mg QD are presented in [Table 9.5-2](#). The combination was well tolerated at the 600 mg BID dose and the 800 mg BID dose of CB-839. The most frequently reported treatment-related AEs (assessed as possibly or probably related to either study drug) were diarrhea, elevations in alanine amino transferase and aspartate amino transferase, decreased appetite, nausea, fatigue, and rash. Grade 3 or Grade 4 events were one event each of Grade 3 diarrhea, Grade 3 hallucination, Grade 3 hypertension, and Grade 4 decreased platelet count, the last of which was the sole dose limiting toxicity (DLT) reported during dose escalation (600 mg BID CB-839 cohort). As with other CB-839 combination

regimens, the recommended Phase 2 dose (RP2D) of CB-839 in combination with full dose cabozantinib was determined to be 800 mg BID. (See [Section 11.1.2](#) for information about cabozantinib monotherapy safety).

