These guidelines are intended primarily for toxicities that investigators assess as *related to study treatment* (CB-839/placebo or cabozantinib) and that are not easily managed with routine supportive care. In general, all AEs should be managed with supportive care at the earliest signs. Dose interruptions of cabozantinib should be as brief as possible.

Unless otherwise specified (see exceptions under Study Drug Dose Modifications above), dose modifications and AE management guidelines presented in this protocol are only recommendations and are not intended to supersede the clinical judgment of the treating physician.

Table 11.1-3: Treatment Modifications Guidelines for Treatment-Related AEs

Toxicity Grade (CTCAE v4)	CB-839/Placebo	Cabozantinib
Grade 1-2	If manageable and tolerable, continue current dose with supportive care.	
	If not tolerable, interrupt dosing and resume at same dose level upon recovery. If Grade 2 toxicity recurs, interrupt and restart at next lower dose.	
Grade 3 (except non-clinically relevant laboratory abnormalities)	Interrupt dosing and resume at the same dose level or next lower dose level upon recovery.	Interrupt dosing, unless toxicity can be easily managed with a dose reduction, and resume at the next lower dose level upon recovery.
Grade 4 (except non-clinically relevant laboratory abnormalities)	Interrupt dosing immediately. Discontinue study drug unless the patient is deriving clear clinical benefit, as determined by the investigator and agreed by the Medical Monitor, and the toxicity can be managed with a dose reduction and optimal medical care.	

11.1.4 Cabozantinib Warnings, Precautions, and Guidelines for Management of Potential Adverse Events

Below are guidelines for the treatment and/or prevention of certain treatment-emergent AEs of interest that have been associated with, or have a theoretical possibility of occurring with, cabozantinib treatment.

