14.7 Safety Analysis

Safety will be assessed by the patient incidence and severity of treatment-emergent adverse events (TEAEs). TEAEs are adverse events (AEs) not present prior to protocol treatment, or an already present event that worsens either in intensity or frequency during or following protocol treatment initiation. The analysis will be performed on the Safety Analysis Patient Set as defined in [Section 14.5.2](#).

TEAEs will be coded by System Organ Class and Preferred Term using the Medical Dictionary for Regulatory Activities (MedDRA). The number and proportion of patients reporting a given TEAE will be tabulated by treatment group according to the worst severity reported. Separate tables will be constructed for a) all reported TEAEs, b) serious TEAEs, and c) TEAEs leading to permanent discontinuation of study treatment. The above tables will also be presented for TEAEs judged to be related (probably or possibility) to the study treatment.

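### For harms that the protocol describes with several MedDRA terms, the planned adverse event tables do not give patient-level incidence by arm; a short pre-fixed grouped table would (cheap improvement)

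*SAP*

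**What the plan says.** SAP 6.7.2 maps verbatim adverse events to MedDRA "preferred terms and system organ classes, and graded by the investigator according to NCI CTCAE v4.03". It continues: "Treatment-emergent adverse events (TEAEs) will be summarized by mapped term, appropriate thesaurus level, NCI CTCAE grade, and treatment arm". Which thesaurus level is appropriate is not stated. Separate summaries are planned for serious events, Grade 3 or higher events, events leading to discontinuation or interruption, and related events. The counting rule is: "Multiple occurrences of the same event in a given patient will be counted once at the maximum grade".

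Protocol 14.7 names the same two levels: "TEAEs will be coded by System Organ Class and Preferred Term using the Medical Dictionary for Regulatory Activities (MedDRA"). It assesses safety by patient incidence and severity, and Protocol 5.0 lists a comparison of safety between the arms among the additional objectives.

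Protocol 11.1.4 introduces its management guidance with "Below are guidelines for the treatment and/or prevention of certain treatment-emergent AEs of interest", here events linked to cabozantinib. For the experimental drug, Protocol 9.4.1 says: "Photophobia and related ocular toxicities (e.g., photopsia) have been identified as CB-839-related events". It lists among the most frequent related events "liver function test (LFT) elevations (e.g., AST, ALT), and photophobia".

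Neither document defines an adverse-event-of-interest table, a grouped term or a standard MedDRA query.

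**The concern.** A preferred-term table answers how many patients had a given coded term. For a harm that sites may report under several terms, the clinical question is how many patients had any of them. Row counts cannot be added, because one patient can appear in several rows. System organ class totals do not help, because they include unrelated events.

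The trial adds CB-839 or placebo to cabozantinib in both arms, so a main safety question is whether CB-839 increases harms already known for the combination's components. For the multi-term harms, the planned tables would give scattered rows rather than one incidence per arm. Because the thesaurus level is left open, any grouping made later could be chosen with the results in view.

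**Working it through.** **1. Which named harms span several terms in the protocol's own description.**

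- Rash: 11.1.4.5 lists blisters and erythematous, macular, papular, acneiform and exfoliative forms.
- Arterial thrombotic events: 11.1.4.7 gives transient ischemic attack and myocardial infarction as examples. Venous events are deep vein thrombosis and pulmonary embolism.
- Perforation and fistula, GI and non-GI: 11.1.4.12.
- Liver tests: ALT, AST and bilirubin in 11.1.4.2.
- Stomatitis and mucositis: 11.1.4.1.
- Hemorrhage: 11.1.4.11, headed hemorrhagic events in the plural. Exclusion criterion 2c separately names hematuria, hematemesis and hemoptysis.
- Ocular: photophobia and photopsia in 9.4.1, to be kept distinct from skin photosensitivity.

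Hypertension, proteinuria, hypophosphatemia, palmar-plantar erythrodysesthesia and osteonecrosis of the jaw are essentially single conditions. A preferred-term row shows them well enough.

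**2. What per-term counts leave open.** If terms have counts a, b, … among N patients, the number of patients with at least one term lies between max(a, b, …) and min(a + b + …, N). This needs no assumed rates.

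| Source | Terms and counts | N | Patients with any term |
|---|---|---|---|
| Table 9.5-1, monotherapy | ALT 13, AST 10 | 88 | 13 to 23 (14.8% to 26.1%) |
| Table 9.5-1, monotherapy | ALT 13, AST 10, GGT 7, ALP 6 | 88 | 13 to 36 (14.8% to 40.9%) |
| Table 9.5-2, with cabozantinib | ALT 6, AST 5 | 13 | 6 to 11 (46.2% to 84.6%) |
| Table 9.5-2, with cabozantinib | Mucosal inflammation 3, stomatitis 2 | 13 | 3 to 5 (23.1% to 38.5%) |

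The upper ends need patients to overlap as little as possible. ALT and AST usually rise together, so the truth there is probably nearer the lower end. Table 9.5-2 gives no site for mucosal inflammation.

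**3. Illustration of dilution (rates assumed).** The documents give no figure for adverse event incidence or power, so there is nothing to reproduce. Assume a grouped harm in 8% of one arm and 18% of the other, 208 patients per arm (Protocol 6.0), and a nominal two-sided 5% Fisher test. Split it equally over k terms with no patient in two rows, which is a worst case. The half-width is 1.96 × √[p₁(1−p₁)/208 + p₂(1−p₂)/208].

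| k | Rates per row | Power per row | Difference ± half-width (points) |
|---|---|---|---|
| 1 (grouped) | 8% vs 18% | 84% | 10.0 ± 6.4 |
| 3 | 2.67% vs 6% | 30% | 3.3 ± 3.9 |
| 5 | 1.6% vs 3.6% | 15% | 2.0 ± 3.1 |

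Other assumed rates behave alike. By the normal approximation, 10% vs 20% has 82% power grouped and 34% per row over three terms; 5% vs 12% has 73% and 30%. The chance that at least one row reaches nominal p < 0.05 in the 8% vs 18% case is about 66% with three terms and 57% with five (simulation), with no control for multiplicity.

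**The case against.** The strongest case against is that nothing planned is wrong. System organ class is named alongside preferred term, and the open thesaurus level would permit grouping. Section 11.1.4 is management guidance for the background drug, not a list of safety endpoints. The stated endpoint (type, incidence, severity, seriousness and relatedness) is reported by the planned tables. Grouped counts can be derived from the coded data at any time, and the IDMC sees unblinded safety data. SAP 6.7.3 also tabulates laboratory values. For the ocular risk, photophobia (12 of 88) is the only ocular term in Table 9.5-1, so grouping may add little there.

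Much of this stands and limits the point. But permission to group is not a specification, and deriving groups after unblinding is what a pre-fixed list avoids. The laboratory tables help only partly with the liver group: the graded analytes are described only as selected, grading is by time point rather than worst post-baseline grade, and bleeding, thrombosis, perforation and ocular events are not covered.

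A reader might go further and infer that all the named harms are hidden, that the SAP uses single terms only, or that a real excess would fall below detection. The documents support none of these. Several harms are single conditions, the tabulation levels are wider than one term, and no adverse event test or threshold exists for an excess to miss.

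**Conclusion.** The point holds for the multi-term harms only. For these, the plan does not deliver once-per-patient incidence by arm, although comparing safety is a stated objective. The firm evidence of size is the range left open by the protocol's own counts: 13 to 23 of 88 patients, and 6 to 11 of 13, for ALT or AST elevation. Those are extreme bounds, and they assume only that a patient counts once per term.

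The power figures are illustrative. They depend on assumed rates, a nominal test that the plan does not contain, and an equal, non-overlapping split. The chance that at least one row stands out is well above the per-row figure, so the signal would not necessarily vanish; but no single row would estimate the incidence of the harm.

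This is a cheap improvement. The primary analysis is untouched.

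**What to change.** In SAP 6.7.2 add one descriptive table by arm: patients with at least one TEAE, counted once per patient at maximum grade, shown for any grade, Grade 3 or higher, and serious.

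Limit it to these groups:

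- hemorrhage;
- venous thromboembolism, and arterial thromboembolism;
- GI or non-GI perforation or fistula;
- ALT, AST or bilirubin elevation;
- stomatitis or mucosal inflammation;
- rash;
- photophobia, photopsia and related ocular events, without skin photosensitivity.

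Do not use broad headings such as gastrointestinal disorders as groups, since they would mix unrelated events just as organ class totals do. Fix the preferred-term list for each group before unblinding, using standard MedDRA queries where they exist. Show the risk difference with a 95% confidence interval, stated as not adjusted for multiplicity.

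The cost is one SAP paragraph, a term list and one table from data already coded. The downside is some judgement in the lists, which is the reason to settle them while blinded. No clinical rule changes.

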4.0 CONTACTS

Emergency Contacts

Safety Physician and Medical Monitor

Name: [REDACTED]
Address: [name]
[name]

Phone: [REDACTED]
Mobile: [REDACTED]
Email: [REDACTED]

Calithera Senior Clinical Trial Manager

Name: [REDACTED]
Address: [name]
[name]

Phone (Office): [REDACTED]
Email: [REDACTED]

SAE Reporting Contact

CRO Safety Lead

Name: [REDACTED]
Address: [REDACTED]
Phone (Office): [REDACTED]
Central Safety Office: [REDACTED]

SAE Reporting Details (to be used for submitting the SAE forms):

[REDACTED]
[REDACTED]

CORE PROTOCOL**5.0 OBJECTIVES AND ENDPOINTS**

Primary Objectives	Primary Endpoints
To compare blinded Independent Radiology Committee (IRC)-adjudicated progression free survival (PFS) of patients treated with CB-839 + cabozantinib (CB-Cabo) versus placebo + cabozantinib (Pbo-Cabo) for advanced or metastatic clear-cell RCC (ccRCC)	IRC-adjudicated PFS per Response Evaluation Criteria in Solid Tumors (RECIST) v1.1
Secondary Objectives	Secondary Endpoints
To compare the overall survival (OS) of patients treated with CB-Cabo vs. Pbo-Cabo	Time from randomization to death from any cause
To compare the investigator-assessed PFS of patients treated with CB-Cabo vs. Pbo-Cabo	Investigator-assessed PFS per RECIST v1.1
Additional Objectives	Additional Endpoints
To compare the overall response rate (ORR), Duration of Response (DOR), and Disease Control Rate (DCR) of CB-Cabo vs. Pbo-Cabo	Per RECIST v1.1 (see Section 14.6.3)
To compare the safety and tolerability of CB-Cabo vs. Pbo-Cabo	Type, incidence, severity, seriousness, and study drug-relatedness of adverse events
To investigate the pharmacokinetics (PK) of CB-839, cabozantinib, and the major CB-839 metabolite 110826 using sparse PK sampling	Potential relationship between drug and metabolite exposure and the efficacy and safety, as well as evaluate the possible effect of CB-839 on cabozantinib exposure
To investigate the relationship of genetic variants and response to CB-Cabo vs. Pbo-Cabo	Genetic variants and other biomarkers related to angiogenesis, and metabolic pathways
To compare quality of life (QoL) changes from baseline of patients treated with CB-Cabo vs. Pbo-Cabo	Functional Assessment of Cancer Therapy-Kidney Cancer Symptom Index (FKSI-19) and EuroQol Health questionnaire instrument (EQ-5D-5L)

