The primary inferential PFS comparison between the two treatment arms will take place when a total of 262 events have been observed. Assuming exponential PFS distributions, patient accrual over a period of 15 months, a median PFS of 8 months for the control arm and a hazard ratio of 0.69 in favor of the experimental arm (equivalent to a 45% increase of median PFS to 11.6 months for the experimental arm), it is estimated that a total of 262 PFS events will occur with 7 months of additional follow-up after accrual completion. The primary analysis will use the stratified log-rank test with the randomization stratification factors of prior PD-1/PD-L1 inhibitor therapy (yes vs. no) and IMDC Prognostic Risk Group (favorable vs. intermediate vs. poor). A 2-sided $p < 0.05$ in favor of the CB-839 + cabozantinib experimental treatment will be regarded as a positive result for the study. The experimental over control hazard ratio will be estimated by a stratified Cox proportional hazards model with the same randomization stratification factors. Kaplan-Meier curves will be presented with median estimates to visually display the progression free survival percentages. In addition, as a secondary analysis for the primary endpoint, the above analyses will be repeated with only two levels, i.e. favorable vs. intermediate/poor, for the IMDC Prognostic Risk grouping.

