14.8 Sample Size Estimation

The sample size of 416 patients, randomized 1:1 for CB-839 + cabozantinib vs. placebo + cabozantinib, is anticipated to provide sufficient efficacy data to demonstrate a clinically and statistically significant benefit for CB-839. For the purposes of study design, it is assumed that

the control arm's true median PFS will be approximately 8 months based upon recently published randomized Phase 3 study results with cabozantinib monotherapy (Choueiri 2015), and that the true hazard ratio (HR) favoring CB-839 + cabozantinib over placebo + cabozantinib will be 0.69, corresponding to a clinically significant increase of 45% or 3.6 months from 8 months to 11.6 months.

The proposed study will enroll patients with an accrual period of 15 months and additional follow-up of 7 months. If the control arm's median PFS is 8 months and the true PFS HR of experimental patients to control patients is 0.69, the study will require approximately 208 experimental patients and 208 control patients in order to reject the null hypothesis of equal PFS between the two treatment arms with a power of 0.85. This estimation assumes a 2-sided type I error rate of 0.05, uniform accrual, exponential PFS distributions and the log-rank test for PFS comparison. The expected total PFS event count is 262 under the above assumptions.

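### The adverse-event tables compare arms by crude patient incidence alone, so under the design's own PFS assumptions equal monthly toxicity would show as about 2 to 6 points more on CB-Cabo

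*SAP*

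**What the plan says.** Protocol 5.0 lists, among the additional objectives, "To compare the safety and tolerability of CB-Cabo vs. Pbo-Cabo". Two sections define the AE tables for that comparison.

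- Protocol 14.7: "The number and proportion of patients reporting a given TEAE will be tabulated by treatment group according to the worst severity reported". Separate tables cover serious events, events leading to permanent discontinuation, and related events.
- SAP 6.7.2: treatment-emergent AEs by term, grade and arm, with "Multiple occurrences of the same event in a given patient will be counted once at the maximum grade". Serious, Grade 3 or higher, discontinuation or interruption, and related events are handled the same way.

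The time at risk is set elsewhere. Protocol 7.0 and SAP 4 continue treatment until progression or unacceptable toxicity. Protocol 15.2 and SAP 6.7.2 follow AEs to 28 days after the last dose, or to new anticancer therapy if earlier. The SAP's reporting definition of treatment-emergent extends to the clinical cutoff date. That does not equalise the window, because follow-up still ends with exposure.

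Protocol 14.6.1 puts the control median at 8 months and the PFS hazard ratio at 0.69, an effect it describes as "equivalent to a 45% increase of median PFS to 11.6 months for the experimental arm". SAP 6.7.1 summarises treatment duration, dose and cycles by arm, but does not use them as a denominator for AEs.

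**The concern.** A crude proportion mixes two things: how often an event occurs per month of treatment, and how many months the patient was watched. Here the second depends on efficacy. If CB-839 delays progression as the design expects, its arm is observed for longer and collects more patients with at least one event, even when monthly toxicity is identical. If CB-Cabo patients instead come off all treatment sooner, the same mechanism works in the other direction and can mask added toxicity.

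The shift is systematic. It moves most common, steadily occurring events the same way, and a larger sample would not remove it. A reader comparing the two AE columns has no planned summary that separates toxicity rate from time at risk.

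**Working it through.** **Inputs.** Protocol 14.6.1 and 14.8: medians 8 and 11.6 months, HR 0.69, 208 patients per arm, accrual 15 months plus 7 months of follow-up. SAP 4.2: accrual 16 months plus at least 8. Protocol 15.2: 28-day tail, w = 28/30.4375 = 0.92 months. The documents give no control-arm AE rates, so the AE hazards h = 0.02, 0.05 and 0.10 per month are assumptions.

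**Step 1: the plan's own figure.** Protocol 14.8 states "two treatment arms with a power of 0.85", and "This estimation assumes a 2-sided type I error rate of 0.05, uniform accrual, exponential PFS distributions and the log-rank test". Schoenfeld's formula gives 4(1.960 + 1.036)²/(ln 0.69)² = 261 events; 262 events give power 0.852. Expected events at 15 + 7 months are 208 × (0.695 + 0.565) ≈ 262. The plan's 262 reproduces, so the exponential model is a fair basis for what follows.

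**Step 2: mean time on treatment.** Progression hazards are l = ln 2/8 = 0.0866 and 0.69 × 0.0866 = 0.0598 per month. Follow-up u is uniform from F to A + F (A accrual, F minimum follow-up). Mean time to progression or cutoff is the average over u of (1 − e^(−lu))/l.

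- 16 + 8 months: 8.4 versus 10.1 months, ratio 1.19.
- 15 + 7 months: 8.0 versus 9.5 months, ratio 1.18.

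**Step 3: crude incidence with the same h in both arms, 16 + 8 months.** With no tail, incidence is the average over u of h/(h + l) × (1 − e^(−(h+l)u)). With the tail, it is the average of 1 − e^(−hw) + e^(−hw) × h/(h + l) × (1 − e^(−(h+l)(u−w))). A common stopping hazard for reasons other than progression (0.04 per month, an assumption) is added to l in both arms.

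| h per month | No tail, control vs CB-Cabo | Gap | Gap with 28-day tail | Gap with tail and 0.04 stopping |
|---|---|---|---|---|
| 0.02 | 14.9% vs 17.6% | 2.7 | 2.4 | 1.7 |
| 0.05 | 31.6% vs 36.6% | 5.0 | 4.5 | 3.2 |
| 0.10 | 49.8% vs 56.3% | 6.5 | 5.7 | 4.3 |

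The first gap column is near the upper end because it ignores the tail and all stopping for other reasons. The last two columns are closer to the plan and span about 2 to 6 points.

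**Step 4: where the gap is small or larger.**

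- Uncommon events (control incidence 5 to 10%): 0.6 to 1.8 points across the tail, stopping and timing variants.
- Onset confined to the first 1 to 3 months: about 0.1 to 2 points.
- No cutoff at all (a limit, not the planned analysis): h/(h + l) gives 36.6% vs 45.5% at h = 0.05 and 53.6% vs 62.6% at h = 0.10, about 9 points.

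**Step 5: the reverse direction (illustration, all assumed).** Take no PFS benefit, an extra 0.03 per month stopping of all study treatment on CB-Cabo, and a true 25% higher AE hazard (0.05 to 0.0625). The no-tail formula gives 31.6% vs 32.1%, so the added toxicity almost disappears.

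**Step 6: what the remedies do under equal constant hazard.** Expected first events divided by expected months at risk equals h in each arm, so the exposure-adjusted ratio is 1.00. The 6-month cumulative incidence, with end of treatment as competing event, is h/(h + l) × (1 − e^(−6(h+l))): 20.5% vs 22.0% at h = 0.05 and 36.1% vs 38.6% at h = 0.10. Some 1.5 to 2.5 points remain.

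**The case against.** The other side has several good points.

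- **The AE tables are not the whole safety analysis.** Exposure is summarised by arm and by drug (SAP 6.7.1), laboratory data by time point (6.7.3) and vital signs by change over time (6.7.4). This stands: the criticism applies to the AE tables alone. But a separate exposure table does not give a rate or a time to first event, and laboratory and vital-sign summaries do not cover events such as diarrhea or fatigue.
- **The artefact is modest.** With 208 per arm, one standard error of a difference, √(2p(1 − p)/208), is 4.5 points at 30% incidence and 4.9 at 50%. No AE test or decision rule is specified. This limits the consequence. It does not remove the systematic direction.
- **Stopping CB-839 does not by itself end observation.** A reader might infer that early CB-839 discontinuation would hide its toxicity. The documents do not support that: Protocol 10.3 keeps patients who stop one drug on the other with scheduled visits, and Protocol 15.2 ties AE follow-up to the last dose of all study treatments. Masking needs all treatment to stop early. AEs leading to discontinuation or interruption are also tabulated.
- **Counting a patient once at maximum grade is ordinary practice.** Agreed; that rule is not the defect and would stay.

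**Conclusion.** The point holds as a limit on interpretation. Every planned AE comparison is a crude patient proportion over a window that lengthens with PFS, and nothing planned separates toxicity rate from time at risk. If the design's PFS assumptions hold and the monthly AE hazard is equal and roughly constant at 0.02 to 0.10, CB-Cabo would show about 2 to 6 points more incidence. The gap is about 1 to 2 points or less for uncommon or early-onset events, and the direction could reverse if CB-Cabo patients leave all treatment sooner. The AE hazards and the non-progression stopping rate are assumptions, since the documents give neither.

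Two stronger readings should be resisted. One is that exposure would differ by 45%: that figure is the gain in median PFS, and with the planned cutoff mean time on treatment differs by 18 to 19%. The other is that the trial cannot answer its safety objective: the tables are descriptive, the artefact is about one standard error or less in most scenarios, and exposure by arm will be on view. Primary and key secondary inference are unaffected.

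**What to change.** Keep the crude tables. In SAP 6.7.2, prespecify two additions by arm for any-grade, Grade 3 or higher, serious and discontinuation-leading AEs and for common preferred terms:

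1. Exposure-adjusted first-event rate: patients with the event per patient-month at risk, where time at risk runs to the first event or the end of the AE window, including the 28 days, with a confidence interval for the difference.
2. Cumulative incidence of first event over a fixed window, for example 6 months, with end of the AE window as a competing event.

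The cost is two sets of tables from data already collected, with no change to conduct, sample size or the primary analysis. Each has a weakness. The first assumes a roughly constant hazard. The second reduces the exposure effect without removing it: about 1.5 to 2.5 points remain at 0.05 to 0.10 per month with the window ending at progression. The SAP should say that the two are to be read together, and should fix them before unblinding so that the choice cannot appear driven by the results.
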